2.1 Participants

Fifty-three children were interviewed. Thirty met the inclusion criteria (see figure 1).

Inclusion criteria: CP-patients with spastic diparesis and GMFCS III (these patients demonstrate elevated functionality in the categories of lying/rolling, sitting and crawling), of both genders aged between 4 and 12 years old, who had support from a full-time caregiver, and who were able to feed orally.

Non-inclusion criteria: CP-patients presenting another catabolic disease which could increase the risk of malnutrition (renal, cardiovascular, pulmonary, hepatic or immunological disease), those presenting infections or receiving antibiotic treatment at least 15 days before starting the study. Patients who had received therapy with botulinum toxin or muscle

relaxants in the last 6 months. CP-patients presenting severe gastroesophageal reflux or with any type of surgery performed in the last 9 months and, patients walking by themselves.

[figure not shown]

Fig. 1. CONSORT flow diagram.

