2.2 Group Assignments

The thirty eligible patients were randomly assigned through a sequence of numbers. These were then divided into three groups: 1) Follow-up group (FG, n=10), only their usual diet was monitored; 2) Conventional Group (CG, n=10), were deworming and received the nutritional therapy recommended by the WHO; 3) Intervention Group (IG, n=10), were deworming and received the NSS which consists of a shake based diet with functional ingredients, high levels of vegetables, fruits, cereals, root-vegetables and fish as well as supplementation with glutamine, arginine, folic acid, nicotinic acid, zinc, selenium, cholecalciferol, ascorbic acid, spirulina, protein vegetable, PUFAs n-3 and probiotics (*Saccharomyces Boulardii* (200 mg every 12 hours for 3 days in the basal period and at week 7). All participants received Bobath physical therapy.

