2.3 Procedures

Once the participants were selected, parents and CP-patients were called to explain the protocol and to collect their informed consent forms. Upon entering the study, the nutritional history and GMFM scale qualification was obtained and recorded from each patient. Thereafter CP-patients were randomly allocated into 3 groups (FG, CG and IG). The energy calculation for the CG and IG groups was performed with the Krick formula (50% carbohydrates, 30% lipids, and 20% proteins).

The parents and / or caregivers of the participants were trained on the project, procedures, as well as feeding and supplementation schemes if required. At the beginning of the treatment, the CG and IG groups were dewormed with nitazoxanide at a dosage of 7.5 mg / kg every 12 hours for 3 days.

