2.6 GMFM assessment

The GMFM scale was performed at baseline time and weeks 7 and 13 after intervention. It was applied by CRIT staff. The evaluators were the blind aspect of the study as they did not have access to any information about the treatment each child was receiving.

This scale assesses five general parameters: 1. Lying (decubitus) and rolling over (GMFAV), 2. Sitting (GMFB), 3. Crawling and kneeling (GMFC), 4. Standing (GMFD), 5. Walking (GMFE) and one final total item (GMFF). The scoring system consists of 88 items and each one is valued based on the following criteria: 0= No, 1= start, 2= Partially Complete, 3= Complete, NE= Not evaluated [18-19].

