2.7 Statistical methods

In order to know the type of distribution of the data, the tests of Kolmogorov-Smirnov, D'Agostino-Pearson and Shapiro-Wilk were applied. Analysis of data was performed using

the continuous variables mean and standard deviation were used if the distribution was normal, and if it didn't present normal distribution the median and range were used. Percentages and proportions assessed the ordinal variables. Analysis of data with normal distributions was performed using One-way ANOVA. ANOVA of repeated measurements was used to analyze the intragroup difference. When the distribution did not show normality, Kruskal Wallis test followed by the Dunn post hoc test. and Tukey were applied respectively to post hoc tests. The level of significance was <0.05 in all cases.

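### Section 2.7 names only unadjusted between-arm tests although every child had a GMFM score before allocation; the tests are valid, but precision and protection against chance imbalance are given up with 10 children per arm

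*Combined protocol and SAP*

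**What the plan says.** Section 2.7 gives the comparison for normal data and the use of repeated measures together: "Analysis of data with normal distributions was performed using One-way ANOVA. ANOVA of repeated measurements was used to analyze the intragroup difference". For other data it gives: "When the distribution did not show normality, Kruskal Wallis test followed by the Dunn post hoc test". Tukey is also named among the post hoc tests. One-way ANOVA and Kruskal-Wallis are not labelled as between-arm tests, but that is the natural reading, because repeated measures are assigned to the within-arm question and the abstract reports differences between groups.

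The legible text does not say whether the response is a raw score or a change, or whether the visit is week 7 or week 13. It names no baseline covariate and no group-by-time term. One sentence in section 2.7 breaks off. The lost words are not held against the plan, and this point concerns only the tests that can be read.

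The baseline is available. Section 2.3 says: "Upon entering the study, the nutritional history and GMFM scale qualification was obtained and recorded from each patient", and then: "Thereafter CP-patients were randomly allocated into 3 groups (FG, CG and IG". Section 2.6 adds: "The GMFM scale was performed at baseline time and weeks 7 and 13 after intervention".

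**The concern.** The abstract makes a comparative claim: the intervention group (IG) did better on standing and walking than the follow-up (FG) and conventional (CG) groups. That claim rests on 10 children per arm. With arms this small, chance differences at baseline are common, and a baseline value of the same scale is often the best predictor of the final score. A one-way test of raw scores ignores it. A one-way test of change uses it, but with a fixed slope of one. Because the plan does not say which response was tested, a reader cannot tell how far the result depends on where the arms happened to start. The only analysis stated to use the repeated measurements is within each arm, and that cannot support a claim about differences between arms.

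**Working it through.** The plan gives no power, effect size, SD or correlation, so it has no figure of its own to reproduce.

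**Inputs from the documents.** Three arms of 10 (section 2.2); significance level 0.05 (section 2.7); GMFM at baseline, week 7 and week 13 (section 2.6).

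**Assumptions.** Baseline-to-week-13 correlation r from 0.3 to 0.9; IG shifted by 0.8 SD and the other two arms equal; normal scores with SD 1. Simulated percentages are good to about one point.

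**1. Error variance and power.** Residual variance is 1 for the raw final score, 2(1 − r) for change and 1 − r² for ANCOVA. With one arm shifted by d, the noncentrality of the three-arm F test is 10 × (2/3)d² / variance. For d = 0.8 the numerator is 10 × 0.667 × 0.64 = 4.27. At r = 0.7 this gives 4.27 for raw scores, 4.27/0.60 = 7.1 for change and 4.27/0.51 = 8.4 for ANCOVA. Error degrees of freedom are 27, 27 and 26. Simulated omnibus power:

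| r | Raw | Change | ANCOVA |
|---|---|---|---|
| 0.3 | 40% | 30% | 42% |
| 0.5 | 40% | 40% | 49% |
| 0.7 | 40% | 61% | 67% |
| 0.8 | 40% | 79% | 82% |
| 0.9 | 40% | 98% | 98% |

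Mean half-widths of the IG-CG 95% interval, without multiplicity adjustment, in SD at r = 0.5/0.7/0.9: raw 0.91/0.91/0.91, change 0.91/0.70/0.41, ANCOVA 0.80/0.66/0.41. At r = 0, ANCOVA power is 38.5% against 39.8% for raw scores, a loss of about 1 point.

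**2. Type I error.** Over all randomisations, omnibus type I error is 4.8% to 5.1% for all three analyses.

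**3. Chance imbalance.** The standard error of a baseline difference between two arms is √(2/10) = 0.447 SD. The chance of an IG-CG gap above 0.5 SD in either direction is 2 × [1 − Φ(0.5/0.447)] = 0.264, or 26%. A gap g shifts the raw difference by rg and the change difference by −(1 − r)g. For g = 0.5 and r = 0.7 these are +0.35 and −0.15 SD. ANCOVA removes the shift on average.

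IG-CG false positives given a gap above 0.5 SD and no true effect:

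| r | Raw, Tukey | Change, Tukey | ANCOVA, Tukey | Raw, none | Change, none | ANCOVA, none |
|---|---|---|---|---|---|---|
| 0.5 | 4% | 4% | 2% | 10% | 10% | 5% |
| 0.7 | 6% | 3% | 2% | 13% | 8% | 5% |
| 0.8 | 7% | 3% | 2% | 16% | 7% | 5% |
| 0.9 | 7% | 3% | 2% | 18% | 6% | 5% |

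The Tukey columns are the relevant ones for ANOVA, because the plan names that test. The columns headed none apply only if no multiplicity adjustment is made. The excess is offset in the other 74% of trials. For raw scores at r = 0.7 without adjustment, the rate there is 1.7%, and 0.264 × 13.4% + 0.736 × 1.7% = 4.8%, which is the nominal level within rounding.

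**4. Floored scores.** Items are scored from zero ("each one is valued based on the following criteria: 0= No, 1= start, 2= Partially Complete, 3= Complete") and section 2.1 excludes "patients walking by themselves", so a floor on the walking dimension is plausible. With an assumed 40% of baseline scores at zero and underlying r = 0.5/0.7/0.8/0.9, power is 38% for raw scores, 39/55/71/92% for change and 45/57/70/90% for ANCOVA. With 60% at zero and r = 0.9, it is 80% for change and 77% for ANCOVA. A permutation test of the adjusted model held type I error at 4.6% to 5.3% and had 70% power with a 40% floor and r = 0.8, the same as the parametric ANCOVA.

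**5. Within-arm tests.** If all three arms truly change by the same amount and each within-arm test has 50% power, the arms disagree on significance with probability 1 − 0.5³ − 0.5³ = 75%. A significant change in one arm and not in another is therefore not evidence of a difference.

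**The case against.** The strongest reply is that randomisation makes the named tests valid, so adjustment is an efficiency choice in a trial labelled exploratory. This is correct, and the point is limited accordingly.

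A second reply is that the response may have been change from baseline. The wording permits this, and the abstract speaks of improvement. In that case ANCOVA gains 9 points of power at r = 0.5 (49% against 40%), 6 at r = 0.7 and 3 at r = 0.8, and nothing at r = 0.9. With a floor it can lose slightly at high r. This reply stands in part: the size of the gain cannot be fixed while the response is unnamed.

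Three stronger readings are tempting, and the documents do not support them.

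- A reader might infer that the comparison is biased. It is not: a chance gap is equally likely to favour either arm, and overall type I error is about 5%.
- A reader might take 10% to 18% as the false-positive rate for raw scores after a baseline gap. Those figures ignore the post hoc test the plan names. With Tukey the rates are 4% to 7%. They also depend on a 0.5 SD gap, a cut-off chosen for illustration.
- A reader might infer that imbalance produced the reported benefit. No baseline values are given, so nothing shows that a gap occurred.

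**Conclusion.** The point holds as one of precision and protection against chance imbalance. As far as it can be read, the plan leaves a pre-allocation GMFM score out of its between-arm tests and does not name the response or visit. If raw week-13 scores were compared and r is between 0.5 and 0.9, power for an assumed 0.8 SD effect is 40% where adjustment would give 49% to 98%. If change was compared, the gain is modest up to r = 0.7 and small or nil from 0.8, or slightly negative there with a floor. The power and conditional error figures rest on an assumed r, an assumed effect and assumed score distributions; the reading of section 2.7 does not.

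It should be fixed because the comparative claim is central and the cost is small. It does not show that the reported GMFM differences are wrong. Nor does it bear on the separate report that half of IG and no child in the other groups walked.

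**What to change.** State in section 2.7 that arms are compared by ANCOVA of week-13 GMFM on arm and the baseline value of the same score. Apply it to all five dimensions and the total, so that scores are not chosen because they were reported as significant. Report adjusted IG-CG and IG-FG differences with Tukey-type simultaneous 95% confidence intervals. Where scores are non-normal or floored, use a permutation test of the same adjusted model. Rank-based ANCOVA should not be the default there: in the floor simulations its power was up to about 7 points below Kruskal-Wallis on change (69% against 75% with a 60% floor and r = 0.9, rounded).

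Base comparative statements on these between-arm estimates and not on the within-arm tests. Label any re-run on the existing data as post hoc.

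The cost is SAP wording, a little analysis of data already collected and one degree of freedom, with no new patients or measurements. The possible losses are about 1 point of power if r is near zero, and up to about 3 points against change-score ANOVA with heavily floored scores and high r (77% against 80%).

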Document:

Study protocol and statistical analysis plan

Protocol:

EFFECT OF A NUTRITIONAL SUPPORT SYSTEM (DIET, SUPPLEMENTS AND PROBIOTIC) FOR IMPROVING GROSS MOTOR FUNCTION IN CEREBRAL PALSY. AN EXPLORATORY RANDOMIZED CONTROLLED CLINICAL TRIAL

NCT number:

2014/03001

Date:

March 28, 2014

EFFECT OF A NUTRITIONAL SUPPORT SYSTEM (DIET, SUPPLEMENTS AND PROBIOTIC) FOR IMPROVING GROSS MOTOR FUNCTION IN CEREBRAL PALSY. AN EXPLORATORY RANDOMIZED CONTROLLED CLINICAL TRIAL

Abstract

Background: Most patients with cerebral palsy (CP) are dependent on parents due to the spasticity and limitations in their gross motor function. Additionally, many of them do not respond to physical therapy due to deterioration in their nutritional status, which is secondary to gastrointestinal disorders, parasitosis, dysbiosis and the catabolic state of the disease itself. Evidence suggests that greater independence and better clinical response can be achieved by correcting the nutritional status. However, basic treatments only contemplate the calculation of energy requirements and do not consider important nutrients in particular, supplementation with glutamine, arginine, zinc, selenium, colexicaliferol, nicotinic acid, spirulina, omega 3, ascorbic acid, vegetal protein or even probiotics.

Objective: To determine the effect of using a nutritional support system (NSS) diet, supplements and probiotic on the gross motor function in children with CP with spastic diparesic and Gross Motor Function Classification System III (GMFCS III).

Material and methods: In an exploratory study with controlled clinical trial design, 30 patients were randomly assigned to receive: 1) dietary surveillance and conventional therapy (FG), 2) deworming and WHO diet (CG), or 3) deworming and the NSS (IG). The patients were recruited from the CRIT Tlalnepantla Estado de México. Males and females aged 4-12 years were included with CP and spastic diparesic GMFCS III, and who had a full-time caregiver and whose parents agreed to participate. They were studied for thirteen weeks. Gross motor function was evaluated at baseline and at 7 and 13 weeks after therapy using the GMFM scale.

Results: The IG-treated group presented a significant improvement in standing and walking parameters analyzed in the GMFM compared with FG and CG groups. Fifty percent of the IG-treated patients managed to walk, while in the other groups no patients were able to walk.

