On the other hand, supplementation with probiotics have also been proposed as a therapeutic strategy for alleviating CNS pathologies [11]. In this case, probiotics have been used to stimulate the production of neurotransmitters, memory, neuroregeneration and also for correcting malabsorption [12].

In order to provide CP-patients with the best therapeutic strategy, it is also important to consider the use of several metabolic rescue pathways to produce energy, including lactate and alanine cycles, where glutamine and glutamic acid are the main substrates [13]. Additionally, deficiencies have also been reported in plasma concentrations of iron, folate, niacin, calcium, vitamin D and E, zinc and selenium even in children with CP who were being supplemented [14-15-16].

Finally, it is relevant to take into account that, 3,500 million people in the world are parasitized and of them, mainly are children, increasing the risk of malnutrition in this group of people [17]. This concomitant factor, makes malnutrition, an even more important problem in CP patients.

It can be said, therefore, that there are several factors that need to be addressed in order to establish the best therapeutic strategy for CP. That is why; in the present study, we tested

an integral food system that includes nutrition, metabolic support, deworming and neurological remodeling support.

2. Materials and methods

The exploratory study was designed as a controlled clinical trial which was randomized and blind, whereby sampling was achieved using the design of consecutive cases. CP-patients with spastic diparesis and GMFCS III were enrolled in this study and treated at the Children's Telethon Rehabilitation Center (CRIT) in Tlalnepantla Estado de México. The duration of the study was 13 weeks for each participant.

The trial complied with the principles of the Declaration of Helsinki and the Mexican norm NOM-012-SSA3-2012 for scientific research in humans. This clinical trial was approved by the Committee of Research of the Faculty of Health Sciences of the Universidad Anáhuac México Campus Norte with the number 2014/03001. The parent or guardian and the patient (in the event that they could sign) signed the informed consent letter voluntarily.

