2.5 Follow up

The participants attended CRIT twice a week to receive physical therapy and once a week for a clinical and nutritional checkup where they would hand in their food diaries and their supplement envelopes to be counted to evaluate their adherence to the course of treatment. On days when the patients attended physical therapy, they were supervised to ensure that they had breakfast, mid-morning snack and lunch.

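### Section 2.7 names no analysis set, and its tests use only children with the needed visits, so any selective loss from the intervention arm could favour the NSS

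*Combined protocol and SAP*

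**What the plan says.** - **Allocation (2.2).** "The thirty eligible patients were randomly assigned through a sequence of numbers", with 10 children in each of the three arms.
- **Follow-up (2, Materials and methods).** "The duration of the study was 13 weeks for each participant".
- **Assessments (2.6).** "The GMFM scale was performed at baseline time and weeks 7 and 13 after intervention". The schedule does not depend on staying on treatment. Nor does the section say that a child who stops the shakes is still scored.
- **Adherence (2.5).** Families hand in "their supplement envelopes to be counted to evaluate their adherence to the course of treatment". No use of the count in the analysis is given, and no rule excludes a child because of it.
- **Analysis (2.7).** For change within a group: "ANOVA of repeated measurements was used to analyze the intragroup difference". For the groups: "Analysis of data with normal distributions was performed using One-way ANOVA", with Kruskal-Wallis for non-normal data. The section defines no analysis set, does not commit to analysis as randomised, and has no rule for missing visits.
- **Result (Abstract).** "Fifty percent of the IG-treated patients managed to walk, while in the other groups no patients were able to walk". No numerator or denominator is given, and IG-treated is not defined.

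**The concern.** The tests in 2.7 settle by default a question that the plan should settle in words: which children count. The intragroup test needs baseline, week 7 and week 13. A group comparison at week 13 needs only that visit, or that visit and baseline if change is tested. A child who leaves after week 7 is lost from the first test, present in a week-7 comparison and absent from a week-13 one. A child who misses only week 7 is lost from the intragroup test but stays in the week-13 comparison.

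The burden is also unequal. Section 2.4 gives only the IG three shakes a day with numbered envelopes over the 13 weeks. If children leave because of that burden, they leave mainly from the IG. If those who leave are the ones progressing least, the remaining IG children look better without any effect of the NSS. With 10 per arm, one or two children are enough to matter. The comparison would then no longer have the full protection of randomisation.

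**Working it through.** The plan gives no sample-size calculation, SD or dropout rate, so there is no planned figure to reproduce beyond 3 × 10 = 30, which agrees with 2.2. The loss scenarios below are assumptions.

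**1. Which children each test uses.** A standard repeated-measures ANOVA routine, given 10 simulated children of whom one lacked week 7, refused the data as unbalanced. One-way ANOVA ran on arms of 10, 10 and 9. As an illustration, suppose a fraction m is lost independently at each of weeks 7 and 13:
- children with week 13 = 10(1 − m)
- children with all three visits = 10(1 − m)²
- m = 10%: 9.0 and 8.1 of 10
- m = 20%: 8.0 and 6.4 of 10

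**2. Size of a selective loss.** Assume no true change in any arm, standard normal change scores, correlation ρ between week-7 and week-13 change, and the k IG children with the lowest week-7 change leaving before week 13. The expected lowest three of 10 standard normal values are −1.539, −1.001 and −0.656. The mean of all 10 is zero, so the remaining 10 − k have mean week-7 change equal to minus the sum of the k removed values, divided by 10 − k. Multiplying by ρ gives the bias at week 13.
- k = 2, ρ = 0.7: 0.7 × (1.539 + 1.001)/8 = 0.7 × 0.3175 = 0.22 SD
- smallest case, k = 1, ρ = 0.5: 0.5 × 1.539/9 = 0.09 SD
- largest case, k = 3, ρ = 0.9: 0.9 × (1.539 + 1.001 + 0.656)/7 = 0.41 SD

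Simulation with 40,000 runs per setting, using t-tests at a nominal 5%, gave these false-positive rates:
- k = 2, ρ = 0.7: about 8% for the IG against a fully followed control arm, and about 10% for the within-IG test
- all settings (k = 1 to 3, ρ = 0.5 to 0.9): about 6% to 14% between arms, and about 6% to 24% within the IG

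A likelihood estimate that kept the leavers' earlier scores had a bias of at most 0.004 SD. That follows from the set-up, because leaving was made to depend only on the observed week-7 change.

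**3. The walking result.** Fifty percent of the IG fits 5 of 10. It also fits 4 of 8 if two children were left out. Two-sided Fisher exact tests against 0/10:
- 5/10: 2 × C(10,5)/C(20,5) = 2 × 252/15504 = 0.033
- 4/8: C(8,4)/C(18,4) = 70/3060 = 0.023
- 4/10, the two lost children counted as not walking: 2 × C(10,4)/C(20,4) = 2 × 210/4845 = 0.087

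Against both comparison arms pooled (0/20), 5/10 gives p = 0.0018 and 4/10 gives p = 0.0077.

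**The case against.** A reader might infer that children who stopped the NSS were in fact dropped, and that this produced the reported benefit. The documents do not support that.

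- **No loss is shown.** No legible text reports a withdrawal, a stopped treatment or an exclusion. The CONSORT diagram (Fig. 1) is not visible in this copy and may give losses and numbers analysed by arm, so they cannot be called missing.
- **Stopping is not withdrawing.** GMFM is not conditional on treatment, and all arms attend for physical therapy. A child who gives up the shakes but attends all three assessments stays in every analysis.
- **The repeated-measures ANOVA is not the test behind the headline.** It serves the intragroup difference. The reported IG benefit is between groups, and those tests do not need all three visits.
- **IG-treated may be only the arm's name.** Section 2.2 gives the IG 10 children, and 5 of 10 is the simplest reading of fifty percent. On that reading p = 0.033.
- **The simulation is near a worst case.** It removes exactly the poorest week-7 children, from the IG only, and uses t-tests in place of the planned three-arm and three-visit tests. Even so, the central between-arm error is 8%.

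All five stand as limits on the claim. They do not remove the gap. A child who leaves before week 13 is absent from a week-13 one-way ANOVA or Kruskal-Wallis test as well, so the headline comparison is exposed through its own test. A flow diagram reports losses, but it does not say how they are handled.

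**Conclusion.** The point holds in a limited, conditional form. Section 2.7 fixes no analysis set, and its tests keep only children with the needed visits. If any visit was missed, the tests describe different sets of children. If the loss was selective and mainly in the IG, it favours the NSS: about 0.22 SD and about 8% between-arm false positives in the central example, and 0.09 to 0.41 SD over the range tried. These figures rest on an assumed number of leavers, an assumed correlation and a deliberately unfavourable pattern of leaving. They show sensitivity at 10 per arm and do not estimate what happened.

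The walking result against one comparison arm depends on its denominator: p = 0.033 for 5/10, and 0.087 if fifty percent means 4 of 8 and the two others are counted as not walking. Against both arms pooled it stays below 0.05 either way. If all 30 children were assessed at all visits, no result is affected by missing data. The change is worth making because it is a better method at little cost, not because bias has been shown.

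**What to change.** 1. **Section 2.7, analysis set.** State that all 30 children are analysed in their assigned arm, whatever the envelope count.
2. **Section 2.7, model.** Replace the repeated-measures ANOVA and the single-visit one-way ANOVA with one mixed model for repeated measures. Use arm, visit, arm by visit and baseline GMFM, fit it to all available visits, and apply a small-sample correction. State that it protects only when loss depends on observed scores. A child with no score after baseline adds nothing to this model, so give the number of such children by arm.
3. **Section 2.6.** State that GMFM is scored at weeks 7 and 13 regardless of adherence.
4. **Walking.** Report n of 10 randomised per arm. Add a sensitivity analysis in which any child not assessed counts as not walking. That rule is one choice among several, so it should not be the only analysis.

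**Cost.** A few sentences and a re-run on data already held. Item 3 cannot recover assessments that were not made; for this trial it can only record what was done. The IG estimate may become slightly less favourable, and nothing changes if all 30 children were assessed at all visits.

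### Does Section 2.7 need a rank test for dependent samples when GMFM scores are compared across visits within an arm?

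*Combined protocol and SAP*

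**What the plan says.** Section 2.7 checks the distribution with three normality tests. It then names one-way ANOVA for normal data and gives within-arm change its own method: "ANOVA of repeated measurements was used to analyze the intragroup difference". The next sentence gives the only test for non-normal data: "When the distribution did not show normality, Kruskal Wallis test followed by the Dunn post hoc test". A fragment follows, "and Tukey were applied respectively to post hoc tests", which most naturally pairs Dunn with Kruskal-Wallis and Tukey with ANOVA. The text as available is broken in two places in this section, so lost words cannot be excluded. Neither Friedman nor Wilcoxon signed-rank appears anywhere.

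Section 2.6 makes the within-arm data dependent: "The GMFM scale was performed at baseline time and weeks 7 and 13 after intervention". Section 2.2 puts 10 children in each of three arms. The documents do not rank comparisons as primary or secondary. The Abstract reports a between-arm result: "significant improvement in standing and walking parameters analyzed in the GMFM compared with FG and CG groups".

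**The concern.** The Kruskal-Wallis sentence comes straight after the within-arm sentence and carries no limit on its use. Applied to three visits, it ignores that the same children are measured each time. Stable differences between children then stay in the error term, and real change is easily missed.

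Non-normal scores are plausible. Section 2.6 says of the items that "each one is valued based on the following criteria: 0= No, 1= start, 2= Partially Complete, 3= Complete". Section 2.1 describes enrolled children by saying that "these patients demonstrate elevated functionality in the categories of lying/rolling, sitting and crawling", which suggests ceilings in those dimensions. It also excludes "patients walking by themselves", which suggests a floor on walking.

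Even if Kruskal-Wallis is confined to between-arm use, the plan tests for normality and then offers no separate method for a within-arm score that fails. At stake are the within-arm p-values and any statement that an arm did not change.

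**Working it through.** **1. Which reading fits the text.** Section 2.7 pairs a purpose with a method only once, for repeated-measures ANOVA and within-arm change. Kruskal-Wallis compares independent groups, as one-way ANOVA does. The natural reading is therefore one-way ANOVA or Kruskal-Wallis between arms, and repeated-measures ANOVA within arms. No sentence says that visits were compared by Kruskal-Wallis.

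**2. Inputs.** From the documents: 10 children per arm, 3 visits, 5% level. The documents give no correlation, SD, effect size or power figure, so there is nothing to reproduce. Assumed: correlation between visits r = 0.5 to 0.8, and a shift of 0.8 SD by week 13 with half of it by week 7. The model is x = √r·(child effect) + √(1−r)·(visit error) + (0, 0.4, 0.8), then transformed or cut to the score shape. There were 20,000 simulations per cell.

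**3. Natural reading: validity.** Type I error of repeated-measures ANOVA is 0.5-5.1% over the six shapes, and 0.7-5.8% if correlation falls with time. There is no material inflation.

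**4. Natural reading: power (%) at r = 0.5 / 0.8, all children shifting.**

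| Score shape | Repeated-measures ANOVA | Friedman | Friedman minus ANOVA |
|---|---|---|---|
| Normal | 54 / 92 | 41 / 80 | −13 / −12 |
| Ceiling at +0.5 SD | 35 / 64 | 34 / 63 | −1 / −1 |
| Floor at the mean | 41 / 76 | 36 / 69 | −5 / −7 |
| Half at ceiling | 21 / 37 | 26 / 44 | +5 / +7 |
| Log-normal | 28 / 58 | 40 / 80 | +12 / +22 |
| 84% at floor | 16 / 26 | 21 / 34 | +5 / +8 |

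**5. Natural reading: only half respond.** The Abstract says half of the IG children walked. Assume 5 of 10 gain 2 SD, with r = 0.8. Friedman then has less power in five of the six shapes, for example 49% v 82% (floor at the mean), 41% v 51% (log-normal) and 56% v 60% (84% at floor). The log-normal advantage in step 4 reverses.

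**6. A pattern by hand.** Five children score 0, 0, 0 and five score 0, 2, 4.

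- Repeated-measures ANOVA: visit means are 0, 1, 2. Visit SS = 10 × (1 + 0 + 1) = 20 on 2 df. Each child has residual SS 2, giving 20 on 18 df. F = (20/2)/(20/18) = 9.0, p = 0.002.
- Friedman: rank sums are 15, 20, 25. Squared deviations from 20 total 50. The sum of squared ranks is 5×12 + 5×14 = 130, less 10×3×16/4 = 120, leaving 10. Q = 2 × 50/10 = 10, p = exp(−5) = 0.007.
- Kruskal-Wallis across visits: mean ranks are 10.5, 16.75, 19.25 around 15.5. H = 29 × 10 × (25 + 1.5625 + 14.0625)/1562.5 = 7.54, p = exp(−3.77) = 0.023.
- Exact paired Wilcoxon with five children changing: smallest p = 2/2⁵ = 0.0625. With Holm over three pairs, six changers give 3 × 2/64 = 0.094 and seven give 3 × 2/128 = 0.047, so at least seven must change.

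**7. Literal reading.** Kruskal-Wallis across visits, normal or log-normal scores, r = 0.5/0.7/0.8: type I error 0.6/0.1/0.03% and power 19/16/15%. Friedman has type I error 4.4-4.6% and power 41/62/80%. The error is conservative: it hides change and does not create false positives.

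**8. Between arms.** Kruskal-Wallis at a single visit has type I error 3.9-4.7% over the shapes tried, so it is sound for the comparison the Abstract reports.

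**The case for a change.** The best case for a change is that the gap exists on either reading and costs a sentence or two to close. A reader cannot tell which test produced a within-arm p-value for a non-normal score. If it was Kruskal-Wallis across visits, a non-significant result says little, at 15-19% power. For strongly skewed or heavily capped or floored scores, the natural reading also gives up some power to Friedman, by up to 22 points. The broken sentence does not rescue the plan, because neither Dunn nor Tukey is tied to a rank test for dependent samples.

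The omission stands, and so do the figures. The call for a change does not:

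- The large loss belongs to the less natural reading of a damaged sentence, and nothing shows that it was done.
- The documents show no score distribution and report no within-arm score that failed normality.
- A Friedman rule would need a trigger such as strong skew or pile-up, for which no threshold is available. It would replace one judgement with another.
- With 84% at the floor, Friedman is itself conservative (type I error 1.2-2.2%). For baseline v week 13 at r = 0.8, Friedman followed by Holm-adjusted Wilcoxon has 5% power there, against 23% for repeated-measures ANOVA followed by Tukey.
- The Abstract already reports results. Relabelling the within-arm analysis as corrected would imply an error that has not been shown.

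**Conclusion.** No change is called for. Section 2.7 leaves a detail unstated, but it already names a within-child method for within-arm change, and an analyst would sensibly use it. That method keeps its error rate in every shape tried. Adding Friedman is a trade-off: between +22 and −13 points of power when all children shift, and worse in five of six shapes when half respond (down to 49% v 82%). The between-arm finding is unaffected.

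This rests on reading Kruskal-Wallis as a between-arm test and on assumed correlations, shifts and score shapes that the documents do not give. It would change only if Kruskal-Wallis had in fact been run across visits. Those within-arm results would then understate the evidence for change and would need re-analysis. Nothing in the documents says that this happened.
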